All participants will receive standard care throughout. This may vary with the child's age, diagnosis, functional level and co-morbidities. Our previous work shows that advice related to PA/diet is rarely given with standard care [89]. However, to document any potential co-interventions, all interactions between study participants and their service providers will be recorded on a standard form (see Appendix 6). The study will thus identify any differences in standard care between groups and across sites, and will inform recruitment, stratification and data analysis in the full RCT. We will identify if any service providers have SFC-Peds training. Coaches will not be part of participants' standard care.

Control information

After randomization, all participants will be given basic printed information relating to PA and healthy diets based upon Health Canada's *Eat Well and Be Active Toolkit* (www.health.gc.ca/eatwell-beactive), which has been reviewed for suitability by expert team members (*[name], [name], [name]*). This ensures that all children have exposure to information on healthy habits, thereby meeting our ethical imperative and ensuring a scientifically rigorous control group. It also helps to control for bias of responses on outcome measures (see Appendix 7 for booklet).

Intervention training

Coaches will be clinicians with physiotherapy, kinesiology, therapeutic recreation, dietetics or similar training who have already been trained in SFC-Peds. They will undertake a half day of training from expert team members, including Canadian PA and diet guidelines [90, 91], and their application to children with SB and CP (*[name], [name], [name]*).

Intervention implementation

Children and Teens in Charge of their Health: A feasibility study of solution-focused coaching to foster healthy lifestyles in children and young people with physical disabilities.

Children randomized into the SFC-Peds group ($n=15$) and their parents will be allocated a coach for eight 60-min SFC-Peds sessions over six months. A six month intervention is supported by meta-analyses of health promotion studies for typically developing children [92] and adults [93]. Time is allowed between sessions for children and parents to work on their goals [27, 70] (see Appendix 11 for coaching schedule).

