Intervention Measure of Engagement – Service Provider (PRIME-SP) (see Appendix 11) and will be assessed by the coaches after each coaching session [126].

STUDY OUTCOMES AND PROCEDURES

Study Procedures

After enrollment into the study, participants will complete the following assessments at the time points outlined below (see Appendix 12 for assessment schedule). Children in the SFC-Peds group will receive the eight 60 minute coaching sessions between Time 1 and Time 2.

Assessment Timings

To assess participant retention, the feasibility study will use four assessment points over 12 months as in the planned efficacy trial: **Time 1 Baseline** (immediately preceding randomization); **Time 2** (immediately post-intervention or 6 months post-baseline for control group +/- 2 weeks); **Time 3** (three months post-intervention or 9 months post-baseline for control group +/- 2 weeks); **Time 4** (6 months post-intervention or 12 months post-baseline for control group +/-4 weeks).

Study Assessments

PRIMARY OBJECTIVE: *To evaluate the feasibility and acceptability of conducting a RCT of a novel, brief, coaching intervention (SFC-Peds) for improving and sustaining PA and dietary habits in CWPD.*

Trial feasibility will be assessed using the following pre-identified criteria (as recommended [82]):

Recruitment	2–3 participants/month recruited over 12 months (for target sample size $n=30$)	$\geq 10\%$ recruitment response rate achieved (min. feasible RCT response rate [99])
Attrition	85% participants successfully complete study (i.e. complete T1 & T4 evaluations)	75% participants complete all assessments (i.e. protocol adherence)
Adherence	Successful completers participate in $\geq 75\%$	75% of the participants complete

Children and Teens in Charge of their Health: A feasibility study of solution-focused coaching to foster healthy lifestyles in children and young people with physical disabilities.

	meetings with coach	evaluations in ≤ 2 hrs (to assess burden)
Stratification	Intervention/control groups similar for age and gender	Intervention/control groups comparable on diagnosis and functional mobility
Fidelity	High intervention fidelity (>8/10 on the Solution-Focused Fidelity Instrument [98])	Challenges/ease of remote coaching (coach, child, family report)

Trial acceptability will be explored qualitatively:

Semi-Structured Survey

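### Times 2 to 4 run from the end of coaching in one arm and from baseline in the other, so outcomes and Time 4 completion can cover different elapsed times by arm

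*Combined protocol and SAP*

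**What the plan says.** Assessment Timings places Time 1 in both arms "immediately preceding randomization". From there the anchors differ. The second assessment is due "immediately post-intervention or 6 months post-baseline for control group +/- 2 weeks". The third keeps the two separate anchors and comes a quarter of a year after the second, with the same tolerance. The last assessment has a wider tolerance but again two anchors: "6 months post-intervention or 12 months post-baseline for control group +/-4 weeks".

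Intervention implementation says that coached children "will be allocated a coach for eight 60-min SFC-Peds sessions over six months". Study Procedures adds: "Children in the SFC-Peds group will receive the eight 60 minute coaching sessions between Time 1 and Time 2". The Overview puts coaching in the first half of a 12-month stay in the study, and Assessment Timings describes the intended length in the same way: "the feasibility study will use four assessment points over 12 months as in the planned efficacy trial".

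Three other parts of the plan depend on this schedule. Design gives the control group the job of accounting for maturation, retesting and dropout over the 12 months. Secondary outcomes measures and Data Analyses plan between-group change and Cohen's d with confidence intervals. The feasibility table sets the attrition criterion: "85% participants successfully complete study (i.e. complete T1 & T4 evaluations".

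**The concern.** For a coached child, Time 2 comes after a coach has been allocated, a first in-person session has been held and eight sessions have been delivered. All of this happens after randomisation. A slow start, a missed session or early stopping can therefore move Times 2, 3 and 4 in the coached arm, while the control visits stay fixed to baseline. The main text gives no latest start, no maximum coaching duration, and no rule for placing Time 2 when coaching ends early or late.

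It is also unclear whether the windows apply to coached children. If they do, they would naturally be read as windows around the end of coaching, and these would not limit elapsed time since baseline.

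The control group can account for maturation and attrition only if both arms are observed over the same elapsed time. If they are not, a between-group difference in activity, diet, psychosocial scores or body composition mixes coaching with extra or missing weeks of growth and habit change in children aged 10 to 18. Completing Time 4 would also mean a longer or shorter follow-up in one arm. The plan says the efficacy trial will use the same time points, so the ambiguity would carry over.

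**Working it through.** **Inputs from the documents.** Control visits fall at 6, 9 and 12 months after baseline, with windows of ±2, ±2 and ±4 weeks. Coached visits fall at the end of coaching plus 0, 3 and 6 months. Nominal coaching duration is six months.

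**Assumed inputs.** The documents give no figures for the delay from baseline to the first session (D, months) or the actual length of coaching (L, months). The values below are illustrations.

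**Formulas.** Coached T2 = D + L; T3 = D + L + 3; T4 = D + L + 6. The gap from control is D + L − 6 at each of the three visits.

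**Plan's own schedule.** With D = 0 and L = 6, the coached visits fall at 6, 9 and 12 months and the gap is zero. The stated schedule is reproduced.

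**Windows in months.** One month is 365.25/12 = 30.44 days. Two weeks is 14/30.44 = 0.46 month; four weeks is 28/30.44 = 0.92 month.

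| D | L | Coached T2 / T3 / T4 | Gap | Within control window at T2 and T3? | At T4? |
|---|---|---|---|---|---|
| 0 | 6 | 6 / 9 / 12 | 0 | yes | yes |
| 0.5 | 6 | 6.5 / 9.5 / 12.5 | +0.5 | no | yes |
| 1 | 6 | 7 / 10 / 13 | +1 | no | no |
| 0 | 5 | 5 / 8 / 11 | −1 | no | no |
| 0 | 8 | 8 / 11 / 14 | +2 | no | no |
| 1 | 5 | 6 / 9 / 12 | 0 | yes | yes |

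Half a month exceeds 0.46 but not 0.92, so it falls outside the window at Times 2 and 3 only. One month in either direction exceeds both limits. The last row shows that a late start does no harm if the time is made up.

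**Is incomplete coaching foreseeable?** The adherence criterion accepts completers who attend at least 75% of meetings: 0.75 × 8 = 6 sessions. The plan thus expects that some children may not attend all eight, without saying when the intervention ends for them.

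**Retention.** 0.85 × 30 = 25.5, so 26 of 30 children must complete Times 1 and 4. The criterion is for both arms together.

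**With a common anchor.** The nominal gap is zero whatever D and L are. Two visits that each fall within ±2 weeks differ by at most 4 weeks (Times 2 and 3); within ±4 weeks they differ by at most 8 weeks (Time 4).

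**The case against.** The strongest reply is that the plan intends one schedule. Coaching occupies the first six of 12 months, so the clocks coincide by design, and anchoring to the end of coaching suits the aims of measuring responsiveness to coaching and experience after it ends. This is right about intent. A reader might infer that the arms are compared at different elapsed times as planned; the documents do not support that. They support only that the times can diverge.

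Several further points also stand:

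- The size of any slip is unknown. Appendix 11 (coaching schedule) and Appendix 12 (assessment schedule) are cited but were not available, and either may fix session weeks or a latest start.
- A reader might infer that a child who stops coaching at month 3 would have Time 2 three months before controls. That follows only if the intervention ends at the child's last attended session. It could equally mean the end of the planned six-month period. The main text does not say which.
- The attrition criteria are pooled, and Data Analyses rules out inferential statistics. Neither a biased between-arm retention test nor an inflated error rate can be claimed.
- GAS and COPM are collected only in the coached arm and need no matched control clock.
- Recruitment runs over 12 months, so each arm already spans the seasons. This weakens a seasonal argument about the 30-day dietary recall, but does not remove the difference in elapsed time.
- Moving every Time 2 item to a fixed date would do harm. If coaching finished late, the interviews on satisfaction and coaching dose would take place mid-coaching, and Photovoice would start before coaching ended.

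The last point limits the remedy but does not defend the two clocks for measures compared between arms. The question of what happens after coaching is a within-arm one and can keep its own anchor.

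**Conclusion.** The point holds as a risk built into the timing rule. Coached visit dates depend on start-up and adherence after randomisation, and control dates do not. Agreement at 6, 9 and 12 months requires coaching to end six months after baseline. On assumed slips, half a month takes Times 2 and 3 outside the control window, and one month takes all three visits outside. How often this would happen cannot be judged from the documents, and the unavailable appendices may narrow it.

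The consequences are confined to the descriptive between-group effect sizes, what 12-month retention means in each arm, and the schedule handed to the efficacy trial. Sample size and error rates are not affected. The change is worth making because it removes an avoidable difference between arms and brings the comparative measures into line with the plan's own 12-month schedule.

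**What to change.** For the measures compared between arms (activity, diet, psychosocial scales, body composition and the family questionnaire) and for Time 4 completion, set Times 2, 3 and 4 at 6, 9 and 12 months after baseline in both arms. Use the same ±2, ±2 and ±4 week windows, whether or not coaching is complete. Keep the coached-only items (GAS, COPM, interviews and Photovoice) tied to the end of coaching, and state how that end is defined when a child stops early or finishes late. Record the date of the last session, and report its gap to Time 2 and actual elapsed times by arm. The sentence placing all eight sessions between Times 1 and 2 needs matching wording. The coaching schedule itself is untouched.

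The cost is protocol wording and visit scheduling, with no change to sample size or measures. Some coached children will have the comparative measures taken before, or some weeks after, their last session, by roughly the amount that coaching slipped. This may slightly dilute the pre-post responsiveness estimate, and some children may need a separate contact for the coached-only items.

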Primary objective: To evaluate the feasibility (study design, methods, processes) and acceptability (family/child/clinician satisfaction, perceived usefulness) of conducting a RCT of a novel, brief, coaching intervention (SFC-Peds) for improving and sustaining PA and dietary habits in CWPD.

Secondary objective: To determine the responsiveness of selected outcome measures to SFC-Peds coaching over 12 months.

Principal research question: *“Is an efficacy trial to evaluate a six month SFC-Peds intervention to improve PA and dietary habits feasible to implement and acceptable to CWPD and families?”*

APPROACHES AND METHODS

Design: We will use a pilot RCT design [82] with two groups: One group (n=15) will work with a coach trained in SFC-Peds eight times over six months. The other group, the control group (n=15), will receive only standard printed materials at the start of the study. These materials will also be available to the SFC-Peds group to control for bias on study measures. The control group will allow us to control for information, maturation, repeated testing and attrition over the 12 month study [83]. All participants will receive standard care from existing clinicians who will not be delivering the SFC-Peds study intervention. The *feasibility* of trial processes, management, and resources will be assessed quantitatively. The *acceptability* of trial participation and coaching processes will be explored qualitatively. Qualitative enquiry lends insight into potential mechanisms of change and barriers to implementation and is therefore highly recommended when evaluating complex interventions [34].

Sample: Thirty children aged 10–18 inclusive and their parents who live within approximately two hours of Holland Bloorview Kids Rehabilitation Hospital (Toronto, ON) up to Thames Valley Children’s Centre (TVCC) (London, ON) will participate. The sites serve diverse socio-cultural communities.

Children and Teens in Charge of their Health: A feasibility study of solution-focused coaching to foster healthy lifestyles in children and young people with physical disabilities.

Child inclusion criteria:

- i) Between the age of 10 – 18 years inclusive
- ii) Diagnosis of SB or CP
- iii) Has physical capability to execute independent body movement with or without device
- iv) Cognitively able and willing to set PA or dietary goals
- v) Can communicate in English and respond to questions requiring some reflection and insight
- vi) Home internet connection

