Skinfold thickness: Skinfold thickness (SFT) is strongly associated with cardiovascular risk factors in children [136]. Tricep and subscapular skinfold thickness will be assessed, as per best practice [137] using Lange callipers (Cambridge Scientific Industries). Subscapular SFT in particular has

Children and Teens in Charge of their Health: A feasibility study of solution-focused coaching to foster healthy lifestyles in children and young people with physical disabilities.

previously demonstrated excellent test-retest reliability when conducted by skilled practitioners [127, 133]. The Slaughter equation will be used to assess body fat [138].

HOME AND ENVIRONMENT ASSESSMENT (PARENT REPORT):

The Family Eating and Activity Habits Questionnaire (see Appendix 30) is a 32-item parent-report assessment to assess the health behaviours of family members as well as the nature of the home environment [121]. It has high internal consistency (0.76-0.87) and test-retest reliability (0.75-0.89). These data will provide context for the children's behavioural outcomes, and allow us to examine the impact of the coaching on the family over time, which will also be examined in qualitative interviews with parents and children.

Post-Study

Following completion of the study, both child and their parent will be thanked and provided with a \$20 gift card for each visit (\$25 for the final visit) as a token of appreciation. Participants will also be offered volunteer hours. Families will be reimbursed for their parking expenses. Additionally, all participants who have completed all of the assessments will be entered into a prize draw for a gift card of \$150 at the end of the study. Participants and their parents will be asked if they wish to receive a summary of the research once the study is completed.

DATA ANALYSES

Sample characteristics will be summarized using descriptive statistics. Inferential statistics are not used in feasibility studies [82].

PRIMARY OBJECTIVE: Feasibility will be assessed using descriptive statistics using our *a priori success criteria* [82]. We will explore any sample/group differences between completers (complete Time 1 and Time 4 measures) and non-completers. We will also determine if there are sample and

Children and Teens in Charge of their Health: A feasibility study of solution-focused coaching to foster healthy lifestyles in children and young people with physical disabilities.

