SECONDARY OBJECTIVE: Measure responsiveness will be established by pre-post intervention differences using effect sizes (Cohen's *d*) and confidence intervals both within and between groups. It is well accepted to examine mean score changes for clinically significant differences pre and post intervention without calculating statistical significance (e.g. a score change of at least 2 points on the COPM is considered clinically significant [38]). We will therefore be able to assess the potential value of SFC-Peds over receiving printed materials only by examining goal scores over time. Our secondary outcomes will be compared with objective behaviour change (goal attainment) for concordance (e.g. whether successful goal attainment corresponds with increased self-determination). We will examine differences in outcome measures by disability, functional mobility, gender and age.

CHALLENGES

Our intervention (SFC-Peds) is largely virtual to reduce burden and enhance adherence [43]. All participants will receive gift cards for completing assessments to reduce attrition; this is a key feasibility outcome, especially in the control group. To reduce possible biases, participants will not meet during the study and coaches will not be involved in standard care. Standardized training (by 3 certified coaches) will be provided. Assessors will be asked which group they think participants are in; blinding success is indicated by accuracies at or below chance level. If adaptations are needed for the RCT, 'A process for Decision making after Pilot and feasibility Trials' (ADePT) [124] will be followed.

KNOWLEDGE TRANSLATION (KT)

A KT planning template [40] will ensure our findings have maximum reach yet are appropriate for feasibility study outcomes. The plan capitalizes on close collaboration of knowledge users and researchers within our investigative team. Integrated KT is promoted throughout the project by the involvement of clinical, family and knowledge user stakeholders, to ensure that the outputs meet the needs of the end users [125]. Holland Bloorview Research Family Engagement Committee members

Children and Teens in Charge of their Health: A feasibility study of solution-focused coaching to foster healthy lifestyles in children and young people with physical disabilities.

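### The only coaching-attendance criterion is judged among children with Time 1 and Time 4 data, so it does not estimate attendance among all 15 children allocated to coaching

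*Combined protocol and SAP*

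**What the plan says.** The feasibility criteria table is under Study Assessments, Primary Objective, in the combined protocol and SAP. Its Adherence row reads "Successful completers participate in $\geq 75" per cent of the meetings with the coach. The row above, Attrition, fixes what completion means: "85% participants successfully complete study (i.e. complete T1 & T4 evaluations". The Data Analyses section uses the same definition: "We will explore any sample/group differences between completers (complete Time 1 and Time 4 measures) and non-completers".

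The Design section plans coaching for the whole arm: "One group (n=15) will work with a coach trained in SFC-Peds eight times over six months". Study Procedures places it early in follow-up: "Children in the SFC-Peds group will receive the eight 60 minute coaching sessions between Time 1 and Time 2". Assessment Timings puts Time 4 at "6 months post-intervention or 12 months post-baseline for control group +/-4 weeks".

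The table is the decision tool for the primary objective. Data Analyses states: "Feasibility will be assessed using descriptive statistics using our" pre-set success criteria. No other row sets a threshold for session attendance. The Attrition items concern assessments, the second Adherence item concerns how long evaluations take, and the Fidelity items concern how coaching is delivered and experienced. The engagement measure that coaches complete after each session has no threshold.

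**The concern.** Whether a child's coaching attendance counts is decided by something that happens about six months after coaching has ended. A coached child who misses Time 4 is removed from the attendance denominator, however many sessions that child attended.

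An efficacy trial needs to know what share of the planned coaching is received by the children allocated to it. A figure restricted to completers does not estimate that share. If children who disengage from coaching also tend to miss Time 4, the criterion can be met while delivery to the allocated group is poor. If losses come mainly after a full course of coaching, the figure errs the other way.

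The criterion also does not say whether each completer must reach 75% or the completers must do so on average.

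**Working it through.** **Inputs from the documents.** There are 30 children, 15 per arm, and 8 planned sessions per coached child (Design; Study Procedures). The attendance threshold is 75% among completers, and the retention threshold is 85% of participants with Time 1 and Time 4 evaluations (criteria table). The documents give no attendance figure for all allocated children, so there is no stated result to reproduce. The power statement under Sample size is not an input here.

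**Assumptions.** The documents do not say how losses would divide between arms or how many sessions lost children would attend. Both are varied below.

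**Step 1: thresholds.** 0.75 × 8 = 6 sessions. 0.85 × 30 = 25.5, so 26 completers are needed. 26/30 = 86.7% passes with 30 − 26 = 4 losses, and there is no limit per arm.

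**Step 2: children reaching 6 sessions.** Let k of the four losses be coached. Suppose no lost child reached 6 sessions and every coached completer did. The criterion reads (15 − k)/(15 − k) = 100% for any k, while the share of allocated children is (15 − k)/15:

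- k = 2: 13/15 = 86.7%
- k = 3: 12/15 = 80.0%
- k = 4: 11/15 = 73.3% (exact 95% CI 44.9% to 92.2%)

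If some lost children did reach 6 sessions, these shares are higher.

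**Step 3: how likely each split is if loss is unrelated to arm.** All four coached: C(15,4)/C(30,4) = 1365/27405 = 5.0%. Exactly two coached: C(15,2)²/C(30,4) = 11025/27405 = 40.2%.

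**Step 4: planned sessions attended.** There are 15 × 8 = 120 planned sessions. With completers at exactly 6 sessions and lost children at x sessions each, the share is [6(15 − k) + kx]/120. The completer figure is 6/8 = 75% throughout.

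| x per lost child | k = 4 | k = 2 |
|---|---|---|
| 0 | 66/120 = 55.0% | 78/120 = 65.0% |
| 5 | 86/120 = 71.7% | 88/120 = 73.3% |
| 8 | 98/120 = 81.7% | 94/120 = 78.3% |

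In the last row every allocated child reached 6 sessions (15/15), and the completer figure of 75% is too low.

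Higher attendance by completers raises the share. With k = 4, x = 0 and completers at all 8 sessions, it is 88/120 = 73.3%, against 100% among completers.

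**Step 5: each completer or the mean.** With 11 coached completers, four attending 8 sessions and seven attending 5 give 32 + 35 = 67 of 88 sessions, or 76.1%. That passes as a mean and fails if each completer must reach 75%. If none of the lost children reached 6 sessions, only 4 of the 15 allocated children did.

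**The case against.** The strongest reply is that retention and adherence are separate criteria meant to be read together. A child who misses Time 4 already counts against the trial in the Attrition row, over all participants. The plan also compares completers with non-completers, coaches complete forms after every session, and the Challenges section names a decision process (ADePT) that begins "If adaptations are needed for the RCT". Attendance for all 15 children could probably be reported without any design change. This stands as mitigation: the losses may well come to light. But the Attrition row is pooled over arms, the comparison is exploratory with no attendance threshold, and none of these changes the denominator of the attendance criterion.

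A reader might infer three stronger claims that the documents do not support.

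- **That the criterion passes at 11 of 15 as a matter of course.** That count needs retention only just met, all four losses in the coached arm, none of the four at 6 sessions, and the reading that each completer must reach 75%. Nor is it a floor: the Adherence row alone sets no minimum number of completers, and Step 5 gives a lower count.
- **That the completer figure always flatters.** A child can attend all 8 sessions and be lost afterwards, which reverses the bias. Conversely, a child who stops coaching but attends Time 4 still counts.
- **That 11/15 fails a stated mark.** The 75% in the table applies to meetings, not to the share of children, so the plan contains no mark of 12/15.

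**Conclusion.** The concern holds as a defect of the denominator. A pre-set criterion for the primary objective measures coaching attendance in a subgroup selected by a later event, and so does not estimate attendance among all 15 children allocated to coaching.

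The size and direction of the error cannot be fixed from the documents. In the four-loss case with completers at exactly 6 sessions, a completer figure of 75% corresponds to 55% to 72% of planned sessions if lost children attended 0 to 5 each, and to 82% if they attended all 8. With an even split of losses and all completers at 6 or more sessions, at least 87% of allocated children reached 6. The four-loss case has a 5% chance if loss is unrelated to arm, and the documents give no rate for loss related to arm. These are illustrations, not predictions.

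In a descriptive study of 30 children this does not undermine the design, but the criterion should be corrected because the change is cheap.

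**What to change.** Apply the existing 75% criterion to all children randomised to SFC-Peds: total sessions attended divided by total planned (8 per child) must be at least 75%. Count sessions not attended after withdrawal as not attended. Beside it, report the number and proportion of allocated children with at least 6 of 8 sessions and an exact 95% CI. Keep the completer figure as a descriptive addition.

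The child-level proportion matters because a pooled rule can hide uneven attendance. Five children at 8 sessions and ten at 5 give 40 + 50 = 90 of 120, exactly 75%, with only 5/15 reaching 6.

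The Intervention implementation section refers to recording the time taken to achieve goals, but what triggers this is unclear. The plan should say whether sessions not needed because goals were met early count as planned.

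The cost is one table cell and simple counts. Coaches' forms after each session should allow attendance to be counted, but the visible text shows no explicit log, so one may have to be added. The figure may be less favourable, and intervals at n = 15 are wide. A rule on the mean is also laxer than requiring 75% of every completer, and the plan should say so openly.

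Separately and optionally, Time 4 retention could be shown by arm beside the pooled 85% criterion.
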